9.7 Dose-Reduction Schedule

The cohort of 6 participants will have staggered enrollment. A minimum interval of 14 days will occur between MSC injection of a subject and MSC injection in the subsequent subject, during which time there must be no SAEs and no AEs ≥ grade 3 that are probably or definitely attributable to MSC injection. The decision to proceed with enrollment of a subsequent subject within a dose cohort will be made by the PI based on the criteria stated above.

For purposes of possible dose reduction from Dose 0 to Dose -1, dose limiting toxicity is defined as a submandibular pain score > 5 (on a standard 0-10 pain scale) at one-month post-injection OR any serious AE probably or definitely caused by study treatment at any time within one-month post-injection OR any of the toxicities below within 1 month of injection:

- Grade 4 neutropenia > 5 days
- Grade 4 thrombocytopenia, or grade 3 thrombocytopenia with hemorrhage
- Grade 3-4 non-hematological toxicity **except**:
 - Grade 3 nausea, vomiting, and diarrhea lasting < 72 hrs in the absence of maximal medical therapy
 - Grade 4 vomiting and diarrhea lasting < 72 hrs in the absence of maximal medical therapy
 - Grade 3 fatigue < 5 days
 - Grade 3 hypertension in the absence of maximal medical therapy

- Grade 3 rash < 5 days is included as an exception
- Grade 3 metabolic abnormalities such as hypokalemia, hypomagnesemia, hypocalcemia, and hypophosphatemia should only be excepted from the DLT definition if they recover to Grade 1 or less within 48 hours.
- Grade 3 fatigue that persists < 7 days.
- Grade 3 rash that resolves to ≤ Grade 1 within 3 weeks.
- Grade 3 or 4 elevation in serum amylase and/or lipase that are not associated with clinical or radiographic evidence of pancreatitis.
- ≥ Grade 3 electrolyte abnormality that lasts < 72 hours, is not clinically complicated, and resolves spontaneously or responds to conventional medical intervention.
- Grade 3 nausea or vomiting that lasts < 48 hours, and resolves to ≤ Grade 1 either spontaneously or with conventional medical intervention.
- Grade 3 immune related AE (irAE) that resolves to ≤ Grade 1 or to baseline with immunosuppressive therapy within 3 weeks.

Additionally, patient enrollment and treatment will be temporarily halted if any of the following occur, pending review by the UWCCC DSMC and FDA if:

- Any death, irrespective of attribution by the investigator within 30 days of MSC injection
- Any (CTCAE v. 5) of grade 4 or higher
- Any hypersensitivity reaction grade 3 or higher at any time
- Any grade 3 SAE in the first 3 subjects
- Any 2 grade 3 or higher of the same SAE at any time during the study
- 5 or more grade 3 or higher SAEs that are at least possibly related at any time during the study

Dose reduction schedule:

Dose level 0 (10 x 10⁶ MSCs into one submandibular gland) given to 6 patients:

- If 0 or 1/6 patients experience DLT at dose level 0, then the dose escalation portion of a subsequent planned study will begin at dose level 0 (10 (8-12) x 10⁶ MSCs into both submandibular glands) and the study will be completed.
- If 2/6 patients experience DLT at dose level 0, then decrease dose to dose level -1 (5 x 10⁶ MSCs) and continue with unilateral injection at dose level -1.

If needed, Dose level -1 (5 x 10⁶ MSCs) given to 3 patients

- If 0/3 or 1/3 patients experience DLT at this dose level 1 then recruit additional 3 patients at this dose.
 - o If 2/3 patients experience DLT, then treatment is considered not tolerable and the study will be halted.
- If 0/6 or 1/6 patients experience DLT at this dose level, then the dose escalation portion of a subsequent planned study will begin at dose level -1 (5 (4-6) x 10⁶ MSCs into both submandibular glands).
 - o If 2/6 patients experience DLT, then treatment is considered not tolerable and the study will be halted.

Part 1 Dose-Reduction Table.

Dose Level	MSC IMP
-1	5 (4-6) x 10 ⁶ injected into one submandibular gland on Day 1
0	10 (8-12) x 10 ⁶ injected into one submandibular gland on Day 1

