5.5 Rationale for Injection of Second Submandibular Gland

We have achieved our primary objective of evaluating the safety and tolerability of injection of interferon gamma stimulated MSCs into the submandibular gland. No patients have had a DLT within one month of injection. Indeed, only 3 patients reported pain (pain scale rating 1/10) with all 3 patients having resolution of their pain within 4 days. There were no serious adverse events. Now that the safety of this dose level of MSCs has been shown, injection of the contralateral submandibular gland at the same dose level will be undertaken. We are opening a phase I clinical trial in 2023 in which patients undergo bilateral submandibular gland injection with interferon gamma stimulated MSCs. In order to provide the most benefit for patients, bilateral injection is recommended, as this will allow for the regeneration of both submandibular glands, which provide the majority of unstimulated saliva.

Additionally, the UW PACT has demonstrated stability of the cryopreserved MSC IMP after storage (see Appendix 19.4 for stability data). Each patient's MSC IMP was cryopreserved, thawed, culture-rescued, and formulated for injection in the already conducted pilot clinical study. The MSC IMP utilized for the second injection is composed of MSCs that were manufactured and cryopreserved at the same time as the MSCs for the first injection.

Each patient has cryopreserved autologous MSCs sufficient to allow for injection of the contralateral submandibular gland at dose level 0. We will utilize the cryopreserved MSCs for the contralateral gland injection, removing the need for another bone marrow aspiration and culturing of cells. The MSC IMP for the second injection will be identical to the first injection with the exception that these MSCs have been in cryopreservation longer.

6.0 THIS AMENDMENT WILL BE FORWARDED TO THE FDA FOR REVIEW PRIOR TO IMPLEMENTATION. STUDY OBJECTIVES AND ENDPOINTS

Objectives	Endpoints
Primary To evaluate the safety and tolerability of MSCs for subjects with xerostomia after radiation for HNC.	Recommended starting dose of MSCs for a Phase I dose-escalation study, determined by the proportion of subjects experiencing dose-limiting toxicity (DLT), where DLT is defined as: submandibular pain > 5 on a standard 10-point pain scale of 0-10 at 1-month after MSC injection OR any serious AE OR any of the selected toxicities listed in section 9.7 within one-month post-injection.
Secondary	

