10.0 STUDY VISITS AND PROCEDURES

10.1 Study Calendar

The procedures performed at each study visit are listed in the table below.

Procedure/Visit	Screening	Baseline	Obtain MSCs ²	MSC IMP Injection	Follow-up visit						
					3-day phone call ⁹	1-week phone call ⁹	1-month	3-month	6-month	12-month	24-month
Visit window											
Day ± days	- 42 ± 14	- 42 ± 14	- 28 ± 14	0	3 ± 2	7 ± 2	30 ± 10	90 ± 14	180 ± 21	365 ± 21	730 ± 28
Informed Consent	X										
Review Eligibility Criteria	X										
Demographics	X										
Review Concomitant Medications	X				X	X	X	X	X	X	X
Dental Evaluation ⁵		X									
Obtain Medical History		X									
Physical Exam		X					X	X	X	X	X
Vital Signs ¹		X		X ³			X				
Bone Marrow Aspiration			X								
MSC IMP Injection				X							
AE Assessment Including Pain			X	X ⁴	X	X	X	X	X	X	X
Assessment of QoL, Salivary Collection		X					X	X	X	X	X
Ultrasound of Salivary Glands		X						X	X	X	
Collection of Pain Diary ⁶							X				
Blood (for banking)		X					X	X	X	X	X
Complete blood count, PT/INR and PTT, Creatinine		X					X ⁸	X ⁸			
Pregnancy test (urine or serum)			X ⁷	X ⁷							

¹ – Vitals include body weight, pulse rate, body temperature, blood pressure, and respiration rate. Height collected only at baseline.

² – Subjects will be contacted via phone 3 days +/- 2 days post bone marrow aspiration to assess for toxicities from aspiration by study coordinator

³ – Vitals to be obtained pre injection and 30 minutes +/- 10 minutes post injection. Weight only obtained pre injection.

⁴ – Subjects will be asked to verbally rate their pain 30 minutes post MSC administration.

⁵ – Dental examination with x-rays within 6 months of enrollment by patient report

⁶ – Patients without chronic pain will be instructed to refrain from narcotic pain medication for 3 days prior to their scheduled pain assessment. Patients with chronic pain will be instructed not to increase their baseline narcotic pain medication for 3 days prior to scheduled pain assessment.

⁷—Within 7 days prior to MSC collection and confirmation of appropriate contraception prior to injection.

⁸—CBC only during follow up

⁹-Subjects will be contacted via phone 3 days (+/- 2 days) and 7 days +/- 2 days post MSC IMP Injection to assess for toxicities from injection by study coordinator or physician.

Sub study calendar

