13.2 Determination of Sample Size

Patients in this pilot trial will undergo unilateral gland injection per FDA request. Associated 95% confidence intervals will be provided for the toxicity rate. To describe changes in quality of life or salivary function/composition between baseline and post-injection timepoints, separate one-way ANOVA models will be fit to the data for each measured outcome. After fitting the models to the data, comparisons between the timepoints will be calculated using Tukey's method. Due to the short time frame of intervention, we anticipate that adherence to the intervention will be high (>90% of patients will complete all mandatory study components) and that rates of follow-up will be similarly high (i.e., low rates of drop outs or lost to follow-up).

Interim analysis: In this pilot study, there is not a planned interim analysis.

Sample Size: Six to twelve patients will be accrued, depending on toxicity encountered. If 0/6 or 1/6 participants experience a DLT at Dose Level 0, sample size would be six. If 2/6 participants experience a DLT at Dose Level 0, another cohort would be enrolled at Dose Level -1. Sample size would then be up to 12 patients, unless 2 or more patients at Dose Level -1 experience a DLT, at which point the study would be stopped.

Length of follow-up: Patients are observed for DLT after MSC injection, with a follow-up of 4 weeks after injection. Secondary outcomes will be assessed at 24 months (end of study for patients). DLT is defined as: pain > 5 on a standard pain scale of 0-10 at 1-month after MSC injection OR any serious AE within one-month post-injection (probably or definitely caused by study treatment) or other toxicities described in section 9.7.

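### The schedule does not systematically ascertain the laboratory DLTs in section 9.7, so the finding of no DLTs should be stated by component and limited to those assessed

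*Combined protocol and SAP*

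**What the plan says.** Section 9.7 defines the DLTs that decide the starting dose for the later study. Besides pain at one month and serious adverse events, it counts these events within one month of injection:

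- "Grade 4 neutropenia > 5 days";
- "Grade 4 thrombocytopenia, or grade 3 thrombocytopenia with hemorrhage";
- grade 3-4 non-haematological toxicity, with a list of exceptions. Grade 3 metabolic abnormalities such as low potassium or magnesium "should only be excepted from the DLT definition if they recover to Grade 1 or less within 48 hours". A separate exception covers a grade 3 or higher "electrolyte abnormality that lasts < 72 hours, is not clinically complicated" that resolves or responds to treatment.

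Section 13.2 describes DLT observation "with a follow-up of 4 weeks after injection".

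The calendar in section 10.1 lists a blood count, coagulation tests and creatinine at baseline. At 1 and 3 months the same row carries a footnote, "CBC only during follow up". The visit lists in section 10.3 agree. The contacts at days 3 and 7 are telephone calls, and the other blood taken at 1 month is for banking. Electrolytes are not scheduled at any visit.

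Section 5.5 reports "No patients have had a DLT within one month of injection" and treats the safety of the dose level as established. Section 14.3 repeats the result in support of the second injection. Neither says which DLT components were measured.

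**The concern.** The primary endpoint (sections 6.0 and 13.7) is a recommended starting dose read from the DLT proportion. Under section 9.7, 0 or 1 DLT in 6 sends the later study to dose level 0. A patient whose neutrophils, platelets or electrolytes were not sampled in the relevant weeks enters that proportion as having no DLT, just like a patient sampled and found normal. For these components, lack of sampling is counted as lack of toxicity. The plan has no step that separates the two, and the safety statement that justifies the contralateral injection rests on the combined result.

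**Working it through.** **The plan's own precision figure.** The synopsis (3.1) gives a 95% interval of 0-64% for 1 event in 6. The exact Clopper-Pearson interval is 0.4% to 64.1%, so the figure reproduces. For 0 of 6 the exact interval is 0% to 45.9%, and the Wilson interval (the method 13.7 names for the pain tabulation) is 0% to 39.0%. Each assumes that all six patients were fully assessed for every DLT component. The 0 of 6 is itself an inference: 5.5 says no patient had a DLT and 7.1 refers to the 6 subjects.

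**Definition against schedule, first month after injection.**

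| DLT component (9.7) | What is needed | What is scheduled (10.1, 10.3) |
|---|---|---|
| Pain > 5 at one month | Pain rating | Daily diary and visit rating |
| Serious or symptomatic grade 3-4 events | Patient contact | Calls at days 3 and 7, diary, 1-month visit |
| Grade 4 neutropenia > 5 days | Serial neutrophil counts | At most one blood count; a differential is not specified |
| Grade 4 thrombocytopenia, or grade 3 with bleeding | Platelet count at the right time | At most one blood count |
| Grade 3 metabolic or electrolyte events, 48 h and 72 h rules | Serial chemistry | None |

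**Can the one count miss the window?** The visit is allowed on days 20 to 40, which is 21 days.

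- After day 30: days 31-40, 10/21 = 48%.
- After 4 weeks (day 28): days 29-40, 12/21 = 57%.

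The next count is at 3 months. The number of scheduled counts in the window is therefore one or none.

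**Chance that the count falls within a neutropenia episode.** The documents give no onset distribution, so this is an illustration. Assume onset day o uniform on 1-30, count day c uniform on 20-40, and an episode of D days. The count falls within it when o ≤ c ≤ o + D − 1. There are 30 × 21 = 630 pairs.

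- D = 6. For c = 20-30, six onsets qualify each day: 11 × 6 = 66. For c = 31-35, 5 + 4 + 3 + 2 + 1 = 15. Total 81/630 = 12.9%.
- D = 10. For c = 20-30, 11 × 10 = 110. For c = 31-39, 9 + 8 + … + 1 = 45. Total 155/630 = 24.6%.
- Count exactly on day 30: D/30, so 6/30 = 20% and 10/30 = 33%.

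A hit gives one low value. It does not show that the episode lasted more than 5 days; that needs a further sample, which the schedule does not contain.

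**Chemistry.** No post-injection samples are scheduled, so the 48-hour and 72-hour recovery rules have no scheduled data to work on.

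**The case against.** The best defence is that a calendar sets the minimum and does not forbid other tests. A grade 4 count would trigger the enrolment halt in 9.7 and 16.5, and repeat counts could follow. Patients are called twice, keep a daily diary of pain and other events, are examined at one month, and remain under their oncology team. Section 15.8 records all adverse events through the 1-month visit. The product is a single local autologous injection, and the risks named in 14.2 are local effects, infection, nerve damage and hypersensitivity-type reactions, not cytopenias or electrolyte disturbance. Section 13.7 already requires full adverse event listings, and 13.0 leaves table mock-ups to a formal SAP.

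Much of this stands, and it rules out three stronger readings.

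- A reader might infer that the laboratory DLTs cannot be detected at all. The documents do not support that: one count can catch an episode in progress, and clinically prompted tests remain possible. The gap is in systematic ascertainment.
- A reader might add pancreatic enzymes to the list of unmeasured DLTs. Section 9.7 names "Grade 3 or 4 elevation in serum amylase and/or lipase that are not associated with clinical or radiographic evidence of pancreatitis" as an exception to the DLT definition, so missing a silent elevation loses no DLT, and pancreatitis could present clinically.
- A reader might conclude that the 0-1 of 6 decision is wrong. Nothing in the documents indicates that it would change.

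The defence does not answer the mismatch itself. A laboratory abnormality without symptoms prompts no test, and event listings do not show who was sampled.

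**Conclusion.** The point holds as a limit on what the primary result covers. Neutropenia lasting more than 5 days, severe thrombocytopenia, and metabolic or electrolyte toxicity are DLTs by definition, but the schedule does not systematically ascertain them and cannot by itself supply the data for the duration rules. The firm facts are at most one scheduled blood count in the window, possibly none, and no scheduled post-injection chemistry. The 13% and 25% figures (20% and 33% with the count on day 30) depend on assumed uniform onset and visit timing and show only order of size. The results for pain, serious events and symptomatic toxicity stand. For the remaining components, no DLTs means none came to notice, and the documents do not say how many patients were assessed.

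**What to change.** 1. Reconcile section 9.7 with the calendar in 10.1, so that the plan says which DLT components the schedule can assess. The one-month and 4-week statements of the window (9.7, 13.2) and the 48-hour and 72-hour electrolyte exceptions also need reconciling. Which rule applies is for the clinical team.
2. In 13.7 and the formal SAP, tabulate DLTs by component with the number of patients actually assessed for each within the window: pain; serious events; symptomatic grade 3-4 toxicity; neutrophils and platelets, with the count day and whether it fell inside the window; and chemistry, marked as not scheduled, with any clinically prompted results shown.
3. Qualify 5.5 and 14.3 so that the finding of no DLTs is stated for the assessed components only.

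The cost is one table and a narrower safety statement. No extra blood draw is needed. Section 13.0 places the formal SAP before database lock, so the table can be specified there.

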9.8 Supportive Care

Optimal patient care is to be given to all subjects. The subjects will be followed by their head and neck oncology team and dentist during the study.

Pain:

Pain should be managed with over-the-counter analgesics if possible. Recommend scheduling acetaminophen 650 mg q 6 hours (maximum < 4,000 mg) or ibuprofen 400 mg q 6 hours (if no contraindications such as decreased renal function). Should pain persist at level 6/10 or greater, opioid pain medications may be prescribed.

Swelling:

Subjects with treatment-related swelling should first try supportive measures such as cold packs and ibuprofen 400 mg q 6 hours (if no contraindications such as decreased renal function). Should the swelling persist, subjects should present to UW clinic for evaluation by medical provider.

9.9 Dose Delays/Modifications

Not applicable to this single administration protocol.

9.10 Study Procedural Intervention(s) Description

Pre-Intervention Bone Marrow Biopsy for MSC Collection

Each subject will undergo a bone marrow (BM) aspirate in order to obtain MSCs. Subjects will undergo BM aspiration for the collection of approximately 30 mL of BM aspirate in the UW Oncology Clinic by an experienced practitioner. Female subjects will have a urine pregnancy test which must be negative to participate. An IV will be placed for conscious sedation, if needed, and for blood collection following the aspiration procedure. If conscious sedation is chosen by the patient, IV sedative will be administered by a trained nurse who will monitor the subject throughout the procedure and recovery from sedation. For the BM collection procedure, the subject will be placed in a prone or side-lying position and the area over iliac crest will be anesthetized with a local anesthetic. The skin will be scrubbed with chlorhexadine and draped with sterile towels/drapes. Using sterile technique, the physician will insert a harvesting needle and aspirate BM into 2-4 10cc syringes, previously rinsed with 3000 units of heparin, collecting 5-10 ml at a time. After the first syringe is aspirated, the beveled needle may be turned 90 degree for three more turns and the aspiration repeated after each turn. Each syringe filled with bone marrow will be injected into a tube that has been prepared with Na Heparin. The collection tube will be labeled with a unique hMSC bank ID number. When all BM has been collected the harvesting needle will be removed and a dressing will be placed over the aspiration site. If subjects have received intravenous (IV) sedation, they will be observed for at least 1 hour or until fully recovered. In addition, subjects will receive a phone call from the research study coordinator within 3 +/- 2 days to review any potential side effects that might be attributable to the bone marrow aspiration.

MSC IMP Administration

The injection of the MSC IMP into the subject's submandibular gland(s) will be done by an experienced Otolaryngology physician under ultrasound guidance in the ENT clinic. Should one submandibular gland be surgically absent, then MSCs will be injected into only the present gland. (Note that patients with only one submandibular gland may not enroll in Part 1, dose level 0). Subjects will be in a semi-recumbent position and the skin over the submandibular gland(s) will be cleansed with chlorhexidine. The area over the submandibular gland will be anesthetized with an injection of 2 mL of 1% lidocaine with 1:100,000 epinephrine. Using sterile technique with US

guidance to ensure avoidance of intravascular injection into branches of the facial and lingual vessels, the submandibular glands will be injected with 0.5-2 mL of MSCs (depending on dosing level) via a 22 gauge, 1 ½ inch needle. The needle will then be removed and a dressing will be placed over the site.

9.11 Method for Assigning to Treatment Groups

Enrollment will be on a rolling basis per DLT schedule. Patients with only one submandibular gland will not be enrolled into this pilot trial.

9.12 Unblinding Procedures

Not applicable.

9.13 Study Intervention Compliance

Pain diary for the first 1 month and QoL surveys, salivary analysis, and submandibular gland US for follow-up visits at 1, 3, 6, 12, and 24 months.

9.14 Concomitant Therapy

Permitted Concomitant Therapy

Any supportive care will be allowed as concomitant therapy including, but not limited to, salivary substitutes and stimulatory agents. During the screening and all follow-up visits, data on the use of concomitant therapies will be collected. These therapies may affect the study endpoints, as they may improve QoL or other study measures. However, as subjects will likely have been previously using this, stopping the medications would likely bias the results. Gathering information on the therapies they are using prior to the intervention will allow us to analyze the possible effects the concomitant therapies may have on our endpoints.

Patients without chronic pain will be instructed to refrain from narcotic pain medication for 3 days prior to their scheduled pain assessment. Patients with chronic pain will be instructed not to increase their baseline narcotic pain medication for 3 days prior to scheduled pain assessment.

Prohibited Concomitant Therapy

None

